6.4.1. Corticosteroids

To date, corticosteroids use is the only pharmacological intervention that has demonstrated benefit in DMD [[Mendell 1989](#), [Fenichel 1991a](#), [Fenichel 1991b](#), [Griggs 1991](#), [Biggar 2001](#), [Beenakker 2005a](#), [Biggar 2006](#), [Pradhan 2006](#)]. To minimize potential confounding effects of changes in corticosteroid therapy on the interpretation of study results, the use of these medications must be standardized as much as possible during the study.

A stable and standardized corticosteroid regimen should be maintained during the 144 weeks of study drug treatment. Adjustments in corticosteroid dosage for increases in body weight are permitted but are not mandatory. Upward adjustments in corticosteroid dose for increases in body weight or other reasons should follow recommendations provided in Appendix A.

If a patient experiences a concerning corticosteroid-related adverse event (eg. hypertension), interventions or potential adjustments in the corticosteroid dosage may be considered, as detailed in Appendix A. It should be emphasized that reductions in corticosteroid dosage for cosmetic or

other minor reasons should be avoided. Patients who require corticosteroid interruption, dose modification, or reinstatement may remain on study drug therapy.

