Discontinuation of corticosteroid therapy during the study should be avoided unless clinically necessary. In the case of the development of predictable corticosteroid-related side effects, appropriate supportive care should be provided and corticosteroid dosage can be maintained (ie, not increased for the normal increase in body weight). If unacceptable corticosteroid side effects persist, the dosage can be reduced in decrements of ≤ 5 mg total dose for prednisone (≤ 6 mg total dose for deflazacort). Finally, corticosteroid administration can be stopped altogether. Specific recommendations for precautionary interventions for specific corticosteroid-related adverse events are given below.

Acne

In the event of bothersome acne that may be attributable to corticosteroids, the following interventions are recommended:

- Corticosteroids should not be increased to adjust for increases in body weight and the patient should be provided with consultation from a dermatologist for institution of appropriate conventional therapy for acne.
- If the acne is so severe it cannot be managed with appropriate anti-acne measures, dosage reductions of ≤ 5 mg total dose for prednisone (≤ 6 mg total dose for deflazacort) at ~ 6 -8-week intervals can be considered.
- Every attempt should be made to avoid stopping corticosteroids solely for acne; if the patient/family demands that corticosteroids be stopped, see [Section D](#) below for procedures for withdrawal of corticosteroids.

Behavior Changes

Where behavior changes are disruptive to family/school life, the following interventions are recommended:

- The patient and the family should be provided with behavioral support from a child psychologist.
- If the patient is already receiving behavioral advice under the guidance of a child psychologist, the corticosteroid dosage should not be increased to adjust for increases in body weight. Consideration can be given to administering the corticosteroid dose at night instead of in the morning.
- If there is no improvement despite behavioral advice under the guidance of a child psychologist, dosage reductions of ≤ 5 mg total dose for prednisone (≤ 6 mg total dose for deflazacort) at ~ 6 -8-week intervals can be considered.
- If the severe behavioral problems continue to cause unacceptable disruption to school/ family life, corticosteroids may be stopped. See [Section D](#) below for procedures for withdrawal of corticosteroids.

Bone Fractures Due to Osteoporosis

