Corticosteroids should not be stopped suddenly. A tapered reduction in dosage is required to avoid risks of adrenal insufficiency. Tapering of drug dosage should follow the normal clinical practice of taking $\frac{1}{2}$ the regular dose for the first week, $\frac{1}{4}$ the regular dose for the second week, $\frac{1}{8}$ the regular dose for the third week and no study drugs thereafter. All adverse effects possibly due to corticosteroid should be monitored until resolved and patients should be followed closely for symptoms consistent with adrenal insufficiency. Patients who require corticosteroid discontinuation may remain on study drug.

E. Reinstitution of Corticosteroids

In patients who discontinue corticosteroids after following the recommended interventions and corticosteroid dosage modification procedures, reinstatement of corticosteroids is not generally recommended unless adrenal insufficiency is detected. However, if reinstatement of corticosteroids is deemed necessary, the corticosteroid dosage should be lower than the lowest total dose that previously proved intolerable. Patients who require corticosteroid reinstatement may remain on study drug.

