### 5.8.4. Timed Function Tests

Timed function test data (ie, time to stand from supine, time to run/walk 10 meters, time to climb 4 stairs, and time to descend 4 stairs) and change from baseline to each post baseline visit will be summarized descriptively by visit for ambulatory subjects with non-missing baseline timed function tests assessments. Similarly the time to stand from supine, time to run/walk 10 meters, time to climb 4 stairs, and time to descend 4 stairs will also be summarized for each actual age.

Timed function test (TFT) data imputation rules as the following will be used in the summary.

- If time to run/walk 10 meters > 30 sec, then set to 30 sec.
- If time to stand from supine > 30 sec, then set to 30 sec.

The Kaplan-Meier method will be applied to the analysis of age at loss of ambulation. The median age at loss of ambulation will be reported by treatment group in studies 020/020e (ataluren/ataluren, placebo/ ataluren, and overall), corticosteroid use duration (<12 months,  $\geq$ 12 months), and corticosteroid type (deflazacort vs prednisone/prednisolone) at baseline. The Kaplan-Meier curves will also be displayed. The age at loss of ambulation is defined as age of the disease progression reported as the adverse event. The subjects who are ambulatory at the end of study or discontinuation will be censored on the last valid visit date. Age on that date will be used in the analysis.

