### **8.2. Matched Populations**

To compare CINRG with Study 020e, the matched populations are defined in the following table for different endpoints and analyses.

Endpoint/Analysis	Age (Years) at Study Entry	Age (Years) at Assessment	Steroid Use	Ambulation status	Exclude EXON 51 and 45	Baseline value	Visit Year
Age at loss of ambulation	7-14	Not applicable	Cumulative Steroid use duration at each assessment $\geq 6$ months	Ambulatory at study entry	Yes		Not applicable
Piece-wise regression based on FVC	Not applicable	$\leq 19$	Cumulative Steroid use duration at each assessment $\geq 24$ months	Non-ambulatory at each assessment	Yes	Not applicable	$\geq 2012$
%-predicted FVC	7-15	Not applicable	Not applicable	Non-ambulatory at study entry	Yes		Not applicable
%-predicted FEV1	7-15	Not applicable	Not applicable	Non-ambulatory at study entry	Yes		Not applicable
PEF	7-15	Not applicable	Not applicable	Non-ambulatory at study entry	Yes		Not applicable
6MWT	7-15	Not applicable	Cumulative Steroid use duration at each assessment $\geq 6$ months	Ambulatory at study entry	Yes		Not applicable
time taken to run/walk 10 meters	7-15	Not applicable	Cumulative Steroid use duration at each assessment $\geq 6$ months	Ambulatory at study entry	Yes		Not applicable
time taken to stand from supine	7-15	Not applicable	Cumulative Steroid use duration at each assessment $\geq 6$ months	Ambulatory at study entry	Yes		Not applicable
NSAA	7-15	Not applicable	Cumulative Steroid use duration at each assessment $\geq 6$ months	Ambulatory at study entry	Yes		Not applicable

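### SAP 8.2 matches CINRG and Study 020e on cumulative steroid duration and not on current use, so off-steroid time is uncontrolled in both specified comparisons, probably but not certainly in ataluren's favour

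*SAP*

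**What the plan says.** **Matching (SAP 8.2).** One table defines the matched set for both cohorts. For age at loss of ambulation, 6MWT, the 10-metre run/walk, standing from supine and NSAA, the steroid entry is "Cumulative Steroid use duration at each assessment $\geq 6$ months". For the piece-wise FVC regression it is "Cumulative Steroid use duration at each assessment $\geq 24$ months". The row for %-predicted FVC reads "predicted FVC 7-15 Not applicable Not applicable", the last entry being the steroid column; %-predicted FEV1 and PEF have the same entry. No row asks whether the boy is taking steroids at entry or at the assessment.

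**Comparisons (SAP 8.3).** Two are specified: Kaplan-Meier for age at loss of ambulation, and FVC by piece-wise regression, in which observed 020e values are set against values predicted from the CINRG model. Neither is stratified or adjusted for steroid use. Steroid use, duration and type appear in descriptive baseline tables, where CINRG baseline is the first registry visit. The walking and function measures get CINRG-only summaries by age, split by steroid use at baseline.

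**Steroids in Study 020e.** Protocol 6.4.1 says that "corticosteroids use is the only pharmacological intervention that has demonstrated benefit in DMD" and that "A stable and standardized corticosteroid regimen should be maintained during the 144 weeks of study drug treatment". Appendix A adds: "Discontinuation of corticosteroid therapy during the study should be avoided unless clinically necessary". It also allows stopping: "Patients who require corticosteroid discontinuation may remain on study drug".

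**Status.** SAP 8.1 gives the purpose as assessing ataluren's long-term benefit. SAP 1 keeps this analysis out of the CSR.

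**The concern.** A cumulative threshold is a one-way gate. A boy who took steroids for six months and stopped years ago satisfies it at every later assessment, and counts as matched to a boy still on treatment.

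The protocol itself regards steroid changes as a confounder: sections 6.4.1 and 13.2.11 give this as the reason for keeping the regimen uniform. Protocol 2.1 also links steroid treatment to preserved lung function. The factor is thus managed within Study 020e by instruction, but left open in the comparison with an outside cohort for which the documents describe no such instruction.

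If CINRG boys spend more of their matched follow-up off steroids than 020e boys do, CINRG would lose ambulation earlier for that reason alone, and the gap would be read as an ataluren effect. The baseline tables would not show it, because they stop at the first registry visit. SAP 5.5 summarises steroid use during the study for 020e, but section 8 plans no counterpart for CINRG.

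**Working it through.** The documents give no sample size, event count, effect size or off-steroid share for the CINRG comparison, so there is no planned figure to reproduce. The check has two parts.

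**1. Does the rule let stopped boys through?** Cumulative duration at a later assessment is never smaller than at an earlier one. Once it reaches 6 (or 24) months, the criterion is met at every later assessment, whatever the current use. This holds for both cohorts, since the same table defines both.

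**2. What could that do to the loss-of-ambulation comparison?** All inputs here are assumptions:
- q: share of CINRG matched follow-up off steroids
- r: the same share in Study 020e
- h: hazard of losing ambulation off steroids relative to on steroids
- ataluren has no effect

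Treating each cohort's hazard as a weighted average of on- and off-steroid hazards:

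apparent HR (020e vs CINRG) = [(1 − r) + r·h] / [(1 − q) + q·h]

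At h = 2 this reduces to (1 + r)/(1 + q):
- q = 20%, r = 5%: 1.05/1.20 = 0.88
- q = 30%, r = 5%: 1.05/1.30 = 0.81
- q = 30%, r = 30%: 1.30/1.30 = 1.00
- q = 5%, r = 20%: 1.20/1.05 = 1.14

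Varying h:

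| q / r | h = 1.5 | h = 2.0 | h = 2.5 |
|---|---|---|---|
| 20% / 5% | 0.93 | 0.88 | 0.83 |
| 30% / 5% | 0.89 | 0.81 | 0.74 |
| 30% / 30% | 1.00 | 1.00 | 1.00 |
| 5% / 20% | 1.07 | 1.14 | 1.21 |

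The sign follows q − r, and the bias vanishes when q = r.

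**What this could mean for a test.** SAP 8.3 names no test for the Kaplan-Meier comparison, so this is illustration only. With d events and equal allocation, the chance that a two-sided 5% test falsely favours ataluren is Φ(√(d/4)·(−ln HR) − 1.96). For d = 100 and h = 2:
- 20%/5%: 9.8%
- 30%/5%: 18.6%
- equal shares: 2.5%, the nominal rate
- 5%/20%: 0.4%

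**FVC.** The same reasoning gives the route of bias: the CINRG regression supplies the predicted values, so off-steroid CINRG assessments would affect the prediction. The documents give nothing from which to put a size on it.

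**The case against.** The strongest reply is that the direction is not established. The filter applies to both cohorts, so 020e boys who have stopped also pass. The stable regimen is an instruction, not a guarantee, and Appendix A lets boys reduce, stop or restart steroids while staying on ataluren. SAP 5.3 and 5.5 plan for boys not receiving steroids at baseline or during the study. This stands: the bias depends on the difference in off-steroid time, which the documents give for neither cohort.

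A reader might infer that the rule favours ataluren outright, for walking and lung function generally. The documents do not support that:
- Setting the 020e share r to zero overstates the effect. At h = 2 and q = 20% it gives 1/1.20 = 0.83, against 0.88 with r = 5%.
- For 6MWT, the timed tests and NSAA, SAP 8.3 specifies no between-cohort comparison.
- Among lung measures only piece-wise FVC uses cumulative duration. %-predicted FVC, FEV1 and PEF have no steroid criterion at all, which is a separate gap, and 8.3 plans only CINRG summaries by age for them.

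Two further replies carry some weight. The analysis sits outside the CSR, which lowers its importance but does not make the matching sound. And conditioning on steroid use after entry may introduce selection, because stopping can reflect tolerance or disease state. That argues for using post-entry steroid status in sensitivity analyses, not in the main definition of the matched set.

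**Conclusion.** The concern holds for two supplementary comparisons: age at loss of ambulation and piece-wise FVC. In both, boys who have stopped steroids count as matched, and nothing in SAP 8.3 corrects for it.

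Because 020e discourages stopping and no equivalent rule is described for CINRG, an imbalance would more plausibly favour ataluren than not. That is a judgement from the asymmetric instructions, not something the documents show. At h = 2 the illustrated hazard ratios run from 0.81 (30%/5%) through 1.00 (equal shares) to 1.14 (5%/20%), and every input is assumed. For FVC the route is clear and the size unknown.

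The change is worth making because the factor is a known prognostic one and the correction is cheap. It does not bear on the primary safety objective or on the CSR analyses.

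**What to change.** 1. **Loss of ambulation, main analysis.** In SAP 8.2, define the matched set in both cohorts as receiving corticosteroid at study entry with at least 6 months' cumulative use. Keep the present cumulative-only filter as a sensitivity analysis.
2. **Stopping after entry.** Entry matching does not catch this. Report off-steroid time during follow-up in both cohorts, and add a loss-of-ambulation sensitivity analysis with current steroid use as a time-varying factor.
3. **Piece-wise FVC.** Add a sensitivity analysis restricted to assessments made while on steroids, or adjusted for current use, and state that it conditions on a post-entry variable.
4. **Optional.** Stratifying by steroid type is not part of the required change. SAP 5.8.4 already reports 020e age at loss of ambulation by "corticosteroid type (deflazacort vs prednisone/prednisolone) at baseline", and SAP 8.3 tabulates type in both cohorts.

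**Cost.** SAP wording and a re-filter of data already transferred. SAP 8.1 lists steroid use and type among the CINRG data to be analysed, and computing cumulative duration at each assessment already calls for exposure history. It is assumed that this history identifies current use. The downside is fewer matched CINRG boys and somewhat wider intervals.

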13.4.5. Spirometry

Progressive pulmonary dysfunction is a major source of disability and shortened survival

associated with DMD and represents an important target for therapeutic intervention. Natural history data in DMD show that pulmonary values decline more precipitously once patients lose ambulation [Steffensen 2002].

Based on experience at measuring pulmonary function in randomized trials [Mendell 1989, Griggs 1991], it is clear that spirometry testing can be performed practically in multicenter studies enrolling study populations comparable to those to be enrolled into this study. Standard operating procedures for spirometry performance, requiring that spirometric effort is sufficient and that each test is consistent with American Thoracic Society/European Respiratory Society guidelines [Miller 2005a, Miller 2005b] will be used.

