### 8.3. Analyses Based on Matched Populations of CINRG and Study 020e

Demographics and baseline characteristics (age, race, ambulation status, corticosteroid use (yes or no), duration of corticosteroid use, corticosteroid type, baseline 6MWD, baseline time to run/walk 10 meters, baseline time to stand from supine, baseline %-predicted FEV1, %-predicted FVC, PEF, NSAA total score) will be summarized descriptively for CINRG and Study 020e

based on each matched population. The summary will be displayed by corticosteroid use (yes vs no) and cumulative steroid use ( $\geq 12$  months vs  $< 12$  months) for baseline ambulatory and non-ambulatory subjects separately. The baseline is defined as the first visit in CINRG data. The comparison to the natural history data (ie, CINRG data) based on matched subjects will be performed in FVC using piece-wise regression models and age to loss of ambulation using Kaplan-Meier method.

Piece-wise regression models will be applied to log FVC in CINRG and study 020e data, separately, using different ages as the changepoint. The most possible changepoint in terms of age will be chosen at the best model fit (ie, AICC value is the maximal). Scatter plots of log FVC and the most fitted piece-wise regression line will be generated for CINRG and study 020e, separately. Comparison between the observed and predicted FVC in study 020e will be performed using repeated measures analysis of variance to account for within-subject correlation, where the predicted values are based on the regression equation estimated by the best fit regression model based on CINRG data.

In study 020e, the loss of ambulation is defined as the disease progression reported as the adverse event or the time to run/walk 10 meters  $> 30$  seconds, whichever occurs earlier. The event age is the one on the AE start date. The subjects who are ambulatory at the end of study will be censored on the last valid timed function tests assessment date. Age on that date will be used in the analysis. In the CINRG data, the age at the earliest report of the non-ambulation or the time to run/walk 10 meters  $> 30$  seconds, whichever earlier, will be picked as the event age. If subjects in CINRG data do not report non-ambulation, the age at the last report of ambulation will be chosen as the censor age. A sensitivity analysis will be performing based on the loss of ambulation defined only by disease progression AE.

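### The SAP 8.2/8.3 FVC comparison with CINRG is confounded with time since loss of ambulation, so it cannot isolate ataluren benefit and can favour ataluren with no drug effect

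*SAP*

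**What the plan says.** SAP 8.1 states the purpose of the CINRG comparison: to assess ataluren's long-term benefit. SAP 8.2 lists the populations for it: "To compare CINRG with Study 020e, the matched populations are defined in the following table for different endpoints and analyses". The filters therefore apply to both sources.

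The row for the piece-wise FVC regression sets no entry age. It requires age at assessment of 19 or under, at least 24 months of cumulative steroid use at each assessment, exclusion of exons 51 and 45, a visit year of 2012 or later, and an ambulation status of "Non-ambulatory at each assessment". Every other row fixes ambulation status at study entry and gives an entry-age range.

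SAP 8.3 gives the model: "Piece-wise regression models will be applied to log FVC in CINRG and study 020e data, separately, using different ages as the changepoint". Observed 020e FVC is then compared with predicted FVC by repeated measures analysis of variance, "where the predicted values are based on the regression equation estimated by the best fit regression model based on CINRG data". No covariate other than age is named.

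Protocol 13.4.5 says: "Natural history data in DMD show that pulmonary values decline more precipitously once patients lose ambulation". SAP 1 keeps the CINRG analysis out of the clinical study report.

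**The concern.** The protocol itself treats loss of ambulation as the point after which lung function falls faster. Among non-ambulatory boys of a given age, those who stopped walking earlier should then have lower FVC. A line in age alone averages over whatever mix of times since loss the registry contains. If 020e boys of the same age lost ambulation more recently, they will sit above that line whether or not ataluren works.

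This is the only planned FVC test against natural history. A positive result would be read as a long-term pulmonary benefit, and the analysis as written could not separate that reading from a difference in timing.

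**Working it through.** The plan gives no sample size, error rate or effect size for this comparison, so there is no figure to reproduce. The check is a bound from the documents, followed by simulation under no drug effect.

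**Time since loss in each source**
- 020e: Study 020 lasts 48 weeks (Protocol 13.2.2) and 020e up to 144 weeks (Protocol 6.2.1). A boy walking at 020 entry is at most about 48 + 144 = 192 weeks (about 3.7 years) past loss. SAP 5.2 says the sponsor stopped 020e, which shortens this.
- CINRG: most boys are wheelchair-bound by 10 to 14 years (Protocol 2.1). At the upper age of 19, time since loss is typically 19 - 14 = 5 to 19 - 10 = 9 years. The steroid, exon and visit-year filters do not limit it.

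**Simulation A: bias with a sound standard error.** The model is joint, with a piece-wise age line, a cohort term and cluster-robust standard errors, tested two-sided at 5% (the general rule in Protocol 10.3; SAP 8 sets no level). Assumptions: age at loss normal with mean 12.5 and SD 2; 300 registry boys entering at 5-18 with annual visits for 4 years; 220 boys walking at 020 entry at 7-14, with spirometry every 24 weeks from week 48; between-boy SD 0.25 and residual SD 0.08 on log FVC. Mean time since loss was 3.5 years in CINRG and 1.0 year in 020e. Ranges are over repeat runs; with 200 runs the Monte Carlo standard error near 45% is about 3.5 points.

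| Extra FVC decline per year after loss | False FVC excess | False positives |
|---|---|---|
| none | - | 4-8% |
| 3% | +3% | 13-16% |
| 6% | +7% | 39-45% |
| 9% | +11% | 74-76% |

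**Simulation B: the SAP's own test.** Observed minus CINRG-predicted log FVC was tested on boy means, 1000 runs per cell. Assumptions: age at loss mean 12, SD 2; 020 entry at 7-15; 5 years of annual registry visits; the same SDs; three settings (200 CINRG and 220 020e boys followed 2.76 years; the same numbers followed 1.4 years; 400 and 110 boys, 1.4 years). Mean time since loss was 3.7 years in CINRG and 0.9 to 1.35 years in 020e.

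| Extra log-FVC loss per year | False excess | SAP test rejects | Joint model, age only | Joint model with time since loss |
|---|---|---|---|---|
| 0 | about 0% | 8-22% | 5.6-6.5% | 4.5-5.4% |
| 0.02 | about +2% | 11-34% | 7-15% | 4.9-6.7% |
| 0.05 | +6 to +7% | 40-69% | 30-47% | 4.8-5.1% |
| 0.10 | +13 to +14% | 85-98% | 76-94% | 4.4-5.7% |

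From 0.05 upward nearly all rejections favour ataluren.

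**Reading the results**
- Bias is about the extra decline rate times the gap in time since loss at the same age. At 0.05 per year, ln(1.067)/0.05 = 1.3 years. That is smaller than the crude gap of 3.7 - 0.9 = 2.8 years because the age line absorbs part of it.
- The 8-22% at zero extra decline has a different source: the CINRG line is treated as known. In closed form, alpha is about 2(1 - Phi(1.96/sqrt(1 + n020e/nCINRG))), which is 17% at equal numbers and 11% when 020e has half the CINRG number. The joint age-only column removes that source and still shows 30-47% at 0.05.
- Sensitivity at 0.05 (second setting, 61%): SD of age at loss 1.2 gives 35%; between-boy SD 0.35 gives 45%; taking the changepoint at the maximal AICC, as SAP 8.3 literally says, gives 53%.
- With a true harm of 0.05 log units in that setting, observed FVC still averaged 1.1% above the line, and 15% of runs were significant in ataluren's favour.

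Neither simulation applies the steroid, exon or visit-year filters.

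**The case against.** **The test does respond to ataluren.** A reader might infer that it tests only whether time since loss is equal. It does not. The null is equal FVC at a given age among non-ambulatory boys. With timing matched, true effects of 0.05, 0.10 and 0.15 log units were detected in 42%, 85% and 98% of runs. The comparison is confounded, not blind to the drug.

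**The reference is not every non-ambulatory registry visit.** It is also filtered on steroid duration, exon and visit year. This stands as description, but none of these filters fixes time since loss.

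**The entry rule of Study 020 is not stated.** The direction of the bias needs walking boys at 020 entry. Protocol 1.1 says this of Study 007, not of Study 020, and SAP 5.1 and 5.3 provide for boys non-ambulatory at 020e entry. The inference rests on Protocol 10.5.1, which repeats a primary analysis of 6MWD and makes provision for patients who become non-ambulatory. Boys who stopped walking during Study 020 still fall within the 192 weeks. The inference is reasonable, but it is an inference. If 020e had the same pattern of time since loss as CINRG, the SAP test's rejection rate at 0.05 would fall to 10%, and that remainder comes from treating the line as known.

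**The rates are assumed.** Protocol 13.4.5 gives no rate of decline, and age at loss and registry size are also assumed. The simulations show what can happen, not this analysis's error rate.

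**Later loss may itself be a drug effect.** This stands. Selecting boys on loss conditions on a post-treatment event, and adjusting for time since loss removes any benefit that works by delaying it.

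**Consequence is limited.** The analysis is outside the study report, the primary objective is safety, and SAP 8 sets no decision rule.

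**Conclusion.** The concern holds as a confounding problem. The FVC comparison leaves out a variable that the protocol itself calls prognostic and that very probably differs between the sources. On the inferred premise that boys were walking at 020 entry, a higher-than-predicted FVC in 020e cannot be attributed to ataluren and can arise with no drug effect.

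The size is conditional: a false excess of about 3% to 11%, with false-positive rates of about 13-16% to about 75%, for 3% to 9% extra decline per year in a model with a sound standard error. A better standard error alone does not cure it.

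A reader might go further and conclude that the design guarantees a false benefit. The documents do not support that: they state neither the Study 020 entry rule nor any decline rate. The change should be made, in proportion to an analysis that is exploratory and outside the study report.

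**What to change.** In SAP 8.3, add time since loss of ambulation as a predictor in the CINRG regression and in the 020e predictions, keeping all eligible CINRG boys.

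Also report a version limited to boys ambulatory at study entry (020 entry, or first CINRG visit). Use the same entry-age range and the same window of time from entry in both sources: from the first 020e spirometry, about week 48 after 020 entry, to the actual maximum 020e follow-up. Report the distribution of time since loss in each cohort. In simulation with the joint model, both approaches brought the false-positive rate to about 4-9%. If the observed-against-predicted test is kept, the error from treating the CINRG line as known remains and needs its own remedy.

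The cost is SAP wording and a re-run, with three limits to state:
- Entry matching kept only about a third of the registry boys or slightly fewer (61 to 69 of 218 in simulation), so its interval is clearly wider. The visit-year rule may reduce this further.
- For a boy already non-ambulatory at his first CINRG visit, the earliest report used in SAP 8.3 may postdate the true loss. The covariate version needs a recorded loss date, or a sensitivity analysis without these boys.
- Both versions condition on loss of ambulation. Any benefit through delayed loss must be read from the Kaplan-Meier analysis of age at loss.
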